5 STUDY INTERVENTIONS/INVESTIGATIONAL PRODUCTS

Investigators will receive the current versions of the Clinical Investigator's Brochures for *Na-GST-1/Alhydrogel®* and *Na-APR-1 (M74)/Alhydrogel®*, which comprehensively describe all available preclinical and human experience with the experimental vaccines. If relevant new information becomes available during the course of the trial, the investigators will receive the revised Investigator's Brochure(s).

5.1 Study Product Description

5.1.1 Acquisition

Vials of *Na-GST-1/Alhydrogel®*, *Na-APR-1 (M74)/Alhydrogel®*, GLA-AF, ENGERIX hepatitis B vaccine, and sterile saline for injection for this study will be supplied to the study site. *Na-GST-1/Alhydrogel®*, *Na-APR-1 (M74)/Alhydrogel®*, and GLA-AF will be transported to the study site at 0.5°C to 10°C; temperature recording devices will accompany the vaccines at all times during transport to ensure temperature limits have not been violated. ENGERIX hepatitis B vaccine and sterile saline will be purchased at the study site.

5.1.2 Formulation, Packaging, and Labeling

5.1.2.1 *Na-APR-1 (M74)/Alhydrogel®*

Na-APR-1 (M74)/Alhydrogel® is supplied as a sterile milky-white suspension (when shaken slightly). Each 2.0 ml vial contains a 0.1 mg/ml suspension of *Na-APR-1 (M74)* adsorbed to 0.8 mg/mL of *Alhydrogel®* in a solution containing 10 mM imidazole, 150 mM sodium chloride and 0.3% Empigen BB, with pH 7.4 ± 0.1. The maximum dose that will be administered is 100 µg of *Na-APR-1 (M74)*, or 1.0 ml of the final drug product. This volume contains the equivalent of approximately 400 µg aluminum. Lower doses of *Na-APR-1 (M74)* are delivered by injecting smaller volumes of the 0.1 mg/ml suspension: for example, 0.3 ml will be injected to deliver 30 µg *Na-APR-1 (M74)*. For all doses, the ratio of *Na-APR-1 (M74)* to *Alhydrogel®* will therefore remain constant: for the 30 and 100 µg doses of *Na-APR-1 (M74)* the respective amounts of *Alhydrogel®* will be 240 and 800 µg (corresponding to approximately 120 and 400 µg aluminum, respectively). *Na-APR-1 (M74)* protein expression was completed at Fraunhofer Center for Molecular Biotechnology (FhCMB/Newark, DE) and purification and vialing at the Walter Reed Army Institute of Research (WRAIR/[name]). The product conforms to established requirements of purity, sterility, safety, and identity. In this study, each dose of *Na-APR-1 (M74)/Alhydrogel®* will be administered in combination with 5 µg GLA-AF.

5.1.2.2 *Na-GST-1/Alhydrogel®*

Na-GST-1/Alhydrogel® is supplied as a sterile milky-white suspension (when shaken slightly). Each 2.0 ml vial contains 1.35 ml of a 0.1 mg/ml suspension of *Na-GST-1* adsorbed to 0.8 mg/ml of *Alhydrogel®* in a buffer consisting of 10% glucose and 10 mM imidazole, pH 7.4. Glucose acts as an excipient and imidazole as the buffer based on evidence that these components specifically

enhance the stability and solubility of Na-GST-1. The maximum dose that will be administered is 100 µg of Na-GST-1, or 1.0 ml of the final drug product. This volume contains the equivalent of approximately 400 µg aluminum. Lower doses of Na-GST-1 are delivered by injecting smaller volumes of the 0.1 mg/ml suspension: for example, 0.3 ml will be injected to deliver 30 µg Na-GST-1. For all doses, the ratio of Na-GST-1 to Alhydrogel® will therefore remain constant: for the 30 and 100 µg doses of Na-GST-1 the respective amounts of Alhydrogel® will be 240 and 800 µg (corresponding to approximately 120 and 400 µg aluminum, respectively). Na-GST-1/Alhydrogel® was manufactured, formulated and vailed at Aeras Global Vaccine Foundation (Rockville, Maryland, USA).

5.1.2.3 Glucopyranosyl-Lipid A Aqueous Formulation (GLA-AF)

GLA-AF will be supplied to the trial site as a 0.5 mL aqueous solution in multi-dose vials containing 25 µg/mL of GLA without preservative. Appropriate volumes of GLA-AF will be withdrawn from the multi-dose vials using a syringe and added to a vial containing Na-APR-1 (M74)/Alhydrogel®, or vice versa (described in the Investigator's Brochure). The mixture must be administered not more than 24 hours after mixing the GLA-AF with Na-APR-1 (M74)/Alhydrogel®.

5.1.2.4 Saline Placebo

Sterile isotonic (0.9%) sodium chloride solution ("normal saline") for injection will be procured by the study site. Normal saline is a clear liquid. In study subjects randomized to receive Hepatitis B vaccine, normal saline will be administered intramuscularly as placebo in an equal volume to the Hepatitis B vaccine. It will be administered in the deltoid muscle of the arm opposite to the one in which the Hepatitis B vaccine is delivered so that all study subjects receive two injections on each day of vaccination, thus maintaining the study blind.

5.1.2.5 Hepatitis B Vaccine

The Hepatitis B vaccine is a non-infectious subunit viral vaccine derived from hepatitis B surface antigen (HBsAg) produced in yeast cells. The antigen is harvested and purified from fermentation cultures of a genetically modified strain of yeast containing the gene for HBsAg. The purified protein is then adjuvanted with aluminum hydroxide adjuvant. The hepatitis B vaccine is a slightly turbid sterile suspension for intramuscular injection. The vaccine is supplied in single-dose vials, with each vial containing enough vaccine to deliver one 0.5 mL dose. Each 0.5 mL dose contains 10 µg of HBsAg and 250 µg of aluminum as aluminum hydroxide. The product conforms to established requirements for sterility, safety, and identity.

5.1.3 Product Storage and Stability

Vaccines, GLA-AF, and placebo will be stored at the site in a refrigerator at 2°C to 8°C until just prior to administration and will not be frozen; refrigerator temperature will be monitored continuously. All vaccine vials will be stored in the upright position.

5.2 Dosage, Preparation and Administration of Study Intervention/Investigational Product

Doses of Na-GST-1/Alhydrogel® will be prepared by withdrawing appropriate volumes into syringes of appropriate size. The Na-APR-1 (M74)/Alhydrogel® plus GLA-AF formulations will be prepared by adding appropriate volumes of GLA-AF solution to vials of Na-APR-1 (M74)/Alhydrogel®, or vice versa, within 24 hours of vaccination. Doses of the Hepatitis B vaccine and sterile saline control will be prepared by withdrawing 0.5 mL into syringes of appropriate size.

Vaccine doses will be administered by qualified study personnel (a study nurse who will not be involved in further assessment of subjects) in the deltoid muscle of the appropriate arm after disinfecting the skin with an alcohol swab and allowing it to dry.

5.3 Modification of Study Intervention/Investigational Product for a Participant

There will be no dose modifications. If a child's second and/or third dose of study vaccination is deferred, it should be rescheduled to occur within the acceptable protocol-specified window for that visit. If this period elapses, the site must obtain prior approval from the Sponsor to administer the second and/or third study vaccination and the documentation of approval should be filed in the child's chart. Children who do not receive the second and/or third study vaccination will be asked to return for safety assessments and for scheduled venous blood sample collections for immunogenicity testing and will be followed for the duration of the study.

Unblinding can occur upon request of the Independent Medical Monitor or the SMC at any time during the study.

5.4 Accountability Procedures for the Study Intervention/Investigational Product(s)

Study vaccines, GLA-AF, and sterile saline placebo supplies must be received by a designated person at the study site, handled and stored safely and properly, and kept in a secure location to which only the designated individuals have access. Study-site personnel are responsible for maintaining accurate records of the vaccine supplies (i.e., Na-GST-1/Alhydrogel®, Na-APR-1 (M74)/Alhydrogel®, Hepatitis B vaccine, the sterile saline placebo, and GLA-AF) received, the quantities administered to study subjects, and the amounts remaining at the conclusion of the study.

After administration of vaccine or GLA-AF doses, the empty or wasted vials will be accounted for and stored at the study site until monitoring by the study Sponsor or their designee. At the conclusion of the study, all used and unused Na-GST-1/Alhydrogel®, Na-APR-1 (M74)/Alhydrogel®, and GLA-AF vials will be returned to the Sponsor or destroyed on site upon direction from the Sponsor, or maintained at 2 to 8°C until further notice from the Sponsor regarding their disposition.

5.5 Concomitant Medications/Treatments

Administration of any medications, therapies, or vaccines will be recorded on the appropriate data collection form. Concomitant medications will include all medications taken within the 30 days prior to enrollment, 28 days after each dose of study product, and for new-onset chronic medical

conditions through the end of participation in the study for each subject. Prescription and over-the-counter drugs will be included as well as vitamins and supplements.

Use of new medication will prompt an evaluation for the presence of a new diagnosis of chronic medical disease or chronic medical condition.

Medications that might interfere with the evaluation of the investigational product should not be used unless absolutely necessary. Medications in this category include, but are not limited to, glucocorticoids, i.e., high dose oral, parenteral and daily inhaled steroids, and immunosuppressive or cytotoxic drugs. Other than from participation in this study, subjects should not receive experimental agents, including vaccines, for the duration of the study.

The administration of licensed vaccines, should be delayed until 28 days after the last administration of the investigational vaccine.

6 STUDY SCHEDULE

The following sections provide a detailed listing of the procedures and tests to be performed in this study at designated time points. The total volume of blood (approximately 94 mL) to be collected from each participating child over the duration of the trial (which is 13-15 months, depending on the vaccination schedule) is approximately the volume collected when donating one unit of blood and should not compromise the health of the children. See **Appendix A** for the schedule of study procedures.

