6.3 Follow-up

Study Day 1

1. Perform basic history and physical exam (including injection site), emphasizing examination of any acute complaints (i.e., AE data collection).
2. Record vital signs.
3. Obtain a urine sample for metabolomics study.

Study Day 3 +/- 1

1. Perform basic history and physical exam (including injection site), emphasizing examination of any acute complaints.
2. Record vital signs.
3. Obtain a urine sample for metabolomics study.

Study Day 7 +/- 1

1. Perform basic history and physical exam (including injection site), emphasizing examination of any acute complaints.
2. Record vital signs.
3. Obtain blood for anti-Na-GST-1 and anti-Na-APR-1 (M74) antibody assays and cellular immunology assays.
4. Obtain a urine sample for metabolomics study.

Study Day 14 +/- 2

1. Perform basic history and physical exam (including injection site), emphasizing examination of any acute complaints.
2. Record vital signs.

3. Obtain blood for hematology, biochemistry, anti-Na-GST-1 and anti-Na-APR-1 (M74) humoral and cellular immunology assays.
4. Obtain a urine sample for metabolomics study.

Study Day 28 +/- 4

1. Perform basic history and physical exam (including injection site), emphasizing examination of any acute complaints.
2. Record vital signs.
3. Obtain blood for anti-Na-GST-1 and anti-Na-APR-1 (M74) humoral and cellular immunology assays.
4. Obtain a urine sample for metabolomics study.

Study Day 56 +/- 7 (Day of Second Vaccination)

1. Perform basic history (including concomitant medications) and physical exam (including injection site), emphasizing examination of any acute complaints.
2. Obtain blood for hematology, biochemistry, anti-Na-GST-1 and anti-Na-APR-1 (M74) humoral and cellular immunology assays.
3. Obtain a urine sample for metabolomics study.
4. Record vital signs.
5. Administer the vaccine.
6. Observe for at least 1 hour after vaccination to evaluate for immediate adverse reactions.

Study Day 57 (1 day after Second Vaccination)

1. Perform basic history and physical exam (including injection site), emphasizing examination of any acute complaints.
2. Record vital signs.

Study Day 59 (3 +/- 1 days after Second Vaccination)

1. Perform basic history and physical exam (including injection site), emphasizing examination of any acute complaints.
2. Record vital signs.
3. Obtain a urine sample for metabolomics study.

Study Day 63 (7 +/- 1 days after Second Vaccination)

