6.5 Early Termination Visit

The following activities will be performed at the early termination visit for study participants who withdraw, or are withdrawn or terminated from the study:

- Obtain interim medical history by interview of subjects and note any changes since the previous visit.

- All concomitant medications will be recorded on the appropriate data collection form (if within 28 days of child's last vaccination received in the study).
- Information regarding adverse events/Serious Adverse Events will be assessed and recorded on the appropriate data collection form (adverse events will be limited to new-onset chronic medical conditions and SAEs if after 28 days after the third study vaccination).
- A targeted physical examination may be, if indicated based on review of interim medical history.
- Approximately 2.4 mL of venous blood may be collected for safety labs and performed by the clinical laboratory (if prior to the post-vaccination day 14 visit and if not recently obtained per study schedule).
- Approximately 6.2 mL of venous blood may be collected for antibody and cellular assays (if prior to post-vaccination day 14 visit and if not recently obtained).

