APPENDIX A1: SCHEDULE OF EVENTS FOR GROUPS 1A, 2A, 3A

Procedures	Blood Volume	Study Days																					
		Pre 1	0	1	3 ± 1	7 ± 1	14 ± 2	28 ± 4	56 ± 7	57	59 ± 1	63 ± 1	70 ± 2	84 ± 4	112 ± 14	113	115 ± 1	119 ± 1	126 ± 2	140 ± 4	200 ± 14	290 ± 14	380 ± 21
Obtain Informed Consent		X																					
Complete History/Physical		X																					
Interim Clinical Evaluation			X	X	X	X	X	X	X	X	X	X	X	X	X	X	X	X	X	X	X	X	
AE/SAE/AESI Assessment			X	X	X	X	X	X	X	X	X	X	X	X	X	X	X	X	X	X	X	X	
Urine Dipstick + Parasitology		X																					
HCV	1.5 mL	X																					
HBsAg		X																					
HIV		X																					
ALT	1.2 mL	X	X				X		X				X		X				X				
Creatinine		X	X				X		X				X		X				X				
CBC ²		X	X				X		X				X		X				X				
Antibody Assays (serum or plasma)	1.2 mL		X			X	X	X	X			X	X	X	X			X	X	X	X	X	
Cellular Assays	5 mL		X			X	X	X	X			X	X	X	X			X	X	X	X	X	
Daily Blood Volume (mL)		3.9	8.6			2.5	8.6	6.2	8.6			2.5	8.6	6.2	8.6			2.5	8.6	6.2	6.2	6.2	
Total Blood Volume (mL)		3.9	12.5			15	23.6	29.8	38.4			40.9	49.5	55.7	64.3			66.8	75.4	81.6	87.8	94	94
Urine sample for metabolomics		X	X	X	X	X	X	X	X	X	X	X	X	X	X	X	X	X	X	X	X	X	
Stool Examination		X																X				X	
VACCINATIONS			1						2						3								

¹ Completed within 90 days of first vaccination

² CBC safety parameters include WBC, absolute neutrophil count, hemoglobin, and platelet count

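### Blood-volume tables contradict themselves on Days 7, 63 and 119/187 (2.5 mL entered, 6.2 mL needed by the marked assays), so the total per child is 94 or 105.1 mL

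*Combined protocol and SAP*

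**What the plan says.** - Section 6 (Study Schedule) states "The total volume of blood (approximately 94 mL) to be collected from each participating child over the duration of the trial", refers to Appendix A for the detail, and concludes that this amount should do the children no harm.
- Appendix A1 (0,2,4-month groups) lists per-assay volumes: "Antibody Assays (serum or plasma) 1.2 mL" and "Cellular Assays 5 mL". Both assays are marked on Days 7, 63 and 119.
- The daily-volume row of Appendix A1 begins "Daily Blood Volume (mL) 3.9 8.6 2.5 8.6 6.2 8.6". The third value, 2.5 mL, is Day 7. The same 2.5 mL recurs on Days 63 and 119, and the running total ends at 94.
- Appendix A2 (0,2,6-month groups) carries the same fifteen daily volumes, with Day 187 in place of Day 119.
- Section 6.3, Day 7, instructs: "Obtain blood for anti-Na-GST-1 and anti-Na-APR-1 (M74) antibody assays and cellular immunology assays". Days 63 and 119/187 likewise call for humoral and cellular assays.
- Section 6.5 (Early Termination Visit) puts a volume on the pair: "Approximately 6.2 mL of venous blood may be collected for antibody and cellular assays". For the safety laboratory set it says: "Approximately 2.4 mL of venous blood may be collected for safety labs". Section 6.6 repeats 2.4 mL for safety laboratories.

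**The concern.** On three visits the same table gives two different amounts of blood to draw from a child: 2.5 mL from the daily-volume row, 6.2 mL from the assay rows. Section 6.3 agrees with the assay rows. Staff working from the visit list and staff working from the volume row would fill different tubes.

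Either way something in the plan needs correcting. If the assay volumes govern, the total in Section 6 is understated, and that total is what supports the safety statement. If the daily row governs, the cellular sample one week after each vaccination is far below its listed 5 mL. Section 2.2.4 names the cellular response at about 7 days after each vaccination as an exploratory outcome. Section 7.2.2.3 describes cultures with medium alone, a mitogen, each vaccine antigen and crude parasite extract, and Section 10.3 adds proliferation and flow cytometry. Nothing says which of these a smaller sample would serve.

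**Working it through.** **1. Reproduce the plan's figure.** The daily-volume row has fifteen entries: one of 3.9 mL (screening), six of 8.6 mL (Days 0, 14, 56, 70, 112/180, 126/194), five of 6.2 mL (Days 28, 84, 140/208, 200/268, 290/358) and three of 2.5 mL (Days 7, 63, 119/187).

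3.9 + 6 × 8.6 + 5 × 6.2 + 3 × 2.5 = 3.9 + 51.6 + 31.0 + 7.5 = **94.0 mL**

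This matches Section 6 exactly. The printed running totals also carry the 2.5 mL entries at each step (12.5 to 15, 38.4 to 40.9, 64.3 to 66.8).

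**2. Check each daily entry against the assays due.** Inputs: screening serology 1.5 mL (appendices); safety laboratories 2.4 mL (Sections 6.5 and 6.6); antibody 1.2 mL and cellular 5 mL (appendices).

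| Visits | Assays due | Sum (mL) | Entered (mL) |
|---|---|---|---|
| Screening | serology + safety | 1.5 + 2.4 = 3.9 | 3.9 |
| Six visits with safety laboratories | safety + antibody + cellular | 2.4 + 1.2 + 5 = 8.6 | 8.6 |
| Days 28, 84, 140/208, 200/268, 290/358 | antibody + cellular | 1.2 + 5 = 6.2 | 6.2 |
| **Days 7, 63, 119/187** | antibody + cellular | 1.2 + 5 = **6.2** | **2.5** |

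Twelve of the fifteen draws reconcile. Only the three visits one week after vaccination do not.

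**3. Total from the assay rows.** One serology draw, seven safety draws (screening plus six visits) and fourteen antibody-plus-cellular draws:

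1.5 + 7 × 2.4 + 14 × (1.2 + 5) = 1.5 + 16.8 + 86.8 = **105.1 mL**

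**4. Size of the gap.**
- 3 × (6.2 − 2.5) = 3 × 3.7 = 11.1 mL, and 105.1 − 94.0 = 11.1 mL, so the three visits account for all of it.
- Relative to the stated total: 11.1 / 94 = 11.8% more.
- Relative to the assay-based total: 11.1 / 105.1 = 10.6%, the amount by which 94 would fall short.

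**5. The other reading.** If 2.5 mL is drawn and the antibody sample takes its full 1.2 mL, the cellular sample is 2.5 − 1.2 = 1.3 mL, which is 1.3 / 5 = 26% of the listed volume. The 2.5 mL is not the antibody sample alone either: with no cellular draw at those visits the entry would be 1.2 mL and the total 94 − 3 × 1.3 = 90.1 mL.

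**6. Sensitivity to the safety-laboratory volume.** The appendix tables as they can be read show 1.2 mL beside ALT and no 2.4 mL entry. Using 1.2 mL for the whole safety set gives 1.5 + 7 × 1.2 + 86.8 = 96.7 mL, but that value fails to reproduce the 3.9 and 8.6 mL entries and disagrees with Sections 6.5 and 6.6. The 11.1 mL gap does not depend on this choice, because no safety laboratories are due on the three visits.

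Some marks in the readable A2 table are displaced. The counts (seven safety draws, fourteen antibody and cellular draws) are the same as in A1, so the totals hold for both schedules. Neither total includes repeat screening or unscheduled draws.

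**The case against.** The strongest reply is that 94 mL is not a mistake in addition. It is the exact sum of the printed row, and Section 6 reports it faithfully. The 2.5 mL entry appears at all three one-week visits in both appendices and runs through every running total. That regularity fits a deliberately smaller draw at least as well as a slip. On that view the row does state a smaller draw, and only its split between assays is missing. This stands, and it is why the point is a contradiction and not an error in a known direction.

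It does not dispose of the matter. The same tables still list 5 mL for the cellular assay and mark it on those days, Section 6.3 orders both assays, and nothing explains the difference.

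A reader might also infer that the one-week cellular outcome cannot be obtained from 1.3 mL. The documents give no minimum volume or cell count for the cellular assays, so that does not follow. What follows is that the plan does not say what the smaller sample supports. The outcome is exploratory. The secondary IgG outcome, about 14 days after the third vaccination, falls on Day 126/194, where the 8.6 mL entry reconciles.

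Finally, 11.1 mL is spread over a trial of 13 to 15 months. The documents give no body weights and no blood-volume limit, so nothing in them shows that 105.1 mL would overturn the Section 6 safety statement, or settles how the volume should be scaled to a child. What parents were told cannot be judged, because consent pages are not part of the public documents.

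**Conclusion.** The point holds as an internal contradiction. On Days 7, 63 and 119/187 the daily volume is 2.5 mL against 6.2 mL for the assays marked and ordered. The total per child is 94 mL on one reading and 105.1 mL on the other.

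A reader might conclude that 94 mL does not follow from the sampling table, or that it is about 12% too low. The documents support neither. The figure is the table's own row sum, and it is too low only if the 2.5 mL entries are the error. In that case the shortfall is 10.6%; 11.8% is the increase over 94.

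The 105.1 mL assumes full antibody and cellular volumes at every marked visit and 2.4 mL per safety draw. The 1.3 mL assumes the antibody sample is taken in full. The matter is worth correcting because the figure governs how much blood is taken from children and underlies a safety statement. It does not touch the analysis of the primary or secondary outcomes.

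**What to change.** Reconcile Section 6, Section 6.3 and Appendices A1 and A2 in one of two ways. The sponsor and investigators need to say which was intended.

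1. **If the full volumes are drawn:** change the three daily entries to 6.2 mL. The running totals become 3.9, 12.5, 18.7, 27.3, 33.5, 42.1, 48.3, 56.9, 63.1, 71.7, 77.9, 86.5, 92.7, 98.9 and 105.1 mL. Change the Section 6 total to about 105 mL.
2. **If the smaller draw is intended:** keep 94 mL, state in the appendices and Section 6.3 that the cellular sample on Days 7, 63 and 119/187 is 1.3 mL, and list which cellular assays are run on it.

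Use the reconciled total wherever blood volume is given as the basis for child safety, including ethics submissions and any parent material that quotes it. The cost is a correction to text and tables. The first option also means stating a somewhat larger volume; the second means acknowledging a limited set of cellular assays one week after each vaccination.
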